9.4.4 Additional data collection

Patient demographics, mechanism of injury, injury type and severity, transfusion of blood products and admission physiology will be recorded in real-time in the emergency department and operating theatre. Patients will then be followed up on a daily basis for organ dysfunction scoring, presence of infection, development of thrombotic events, surgical episodes and other adverse events until Day 28, discharge or death. All of this data (aside from organ dysfunction scores outside of the critical care unit) is routinely collected in the management of injured trauma patients. No additional monitoring or interventions will be required.

9.4.5 Patient questionnaires

Quality of life assessment will be measured by the use of self reported EuroQol EQ-5D questionnaire and the Extended Glasgow Outcomes Scale (GOS-E) in adults at hospital discharge or Day 28 (whichever is sooner) and again at one year following injury (see Section 9.6 for follow up data collection). In paediatric patients, quality of life will be measured using the Paediatric Quality of Life Inventory (PedsQL) questionnaire that corresponds with the age of the child at the time of injury. Assessment will be carried out at the same time points as for ACIT Protocol V8 16.07.2024

adults. Health economic implications of massive transfusion and resource use will be collected with an additional questionnaire at the one year follow up.

The in-hospital questionnaire will be conducted by research staff with the patient where possible, but may also be completed with the patient's personal consultee if necessary. The questionnaire can be completed in less than five minutes.

9.5 Procedure for collecting data (Case Report Forms)

Data collection for this study will be accomplished using a paper case report form (CRF) to capture data prospectively and transferred to an electronic data capture system (RedCap). CRFs are required and will be completed for each participant. It is the Investigator's responsibility to ensure the accuracy, completeness and timeliness of the data reported on the subjects CRF. CRFs will be completed in a timely fashion to support the study timelines. Future prospective data collection may be possible with validated and JRMO approved electronic data capture methods e.g. REDCap and ultimately supersede paper CRF.

9.6 Follow-up procedures

The 12-month EuroQol EQ-5D (adults) or PedsQL (paediatrics) patient questionnaire will be posted or emailed to surviving patients along with a return stamped addressed envelope. The questionnaire provides instructions for completion of the whole questionnaire, which will take approximately five minutes. Patients who have not returned the questionnaire within two weeks of the initial request will be telephoned as a reminder to complete the questionnaire and may be asked to complete it over the phone if necessary. A maximum of three recorded contact attempts will be made via phone and if these are unsuccessful, no further contact will be made and responses will be marked as not returned. Confirmation with the GP and scrutiny of the hospital care record system will ensure only those patients alive at 12 months receive a questionnaire.

9.6. Laboratory assessments

Measures of whole blood functional coagulation will be performed using equipment at the Point-of-Care and within the research laboratory. Whole blood functional testing will be performed with rotational thromboelastometry. Coagulation markers to be tested will include:

Prothrombin fragments 1+2, Protein C, Endothelial Protein C Receptor (EPCR),

Thrombomodulin, Tissue factor, Plasminogen Activation Inhibitor-1 (PAI-1), tissue

Plasminogen Activator, Tissue factor Activatable Fibrinolysis Inhibitor (TAFI), D-Dimers and

S100A10. Markers for endothelial injury will include von Willibrand Factor (vWF) and Eselectin.

Platelet function and activation tests will include: 96-well light transmission aggregometry, Multiplate impedance aggregometry, flow cytometry and imaging studies.

Inflammation markers will include TNF- α , IL-1,IL-6,IL-8,IL-10, Complement components, heat shock proteins. Samples will also be processed and stored for DNA, RNA and proteomic analyses. Samples will also be available for leukocyte phenotyping with flow cytometry.

9.7. Patient withdrawal

Each participant has the right to withdraw from the study at any time and for any reason without prejudice to his or her future medical care by the Investigator or at the institution.

Every reasonable effort will be made to maintain protocol compliance and to retain patient participation in the study consistent with the provisions of informed consent and good clinical practice. Additionally the PI may withdraw the participant. The following are potential reasons why a patient may be withdrawn from the study:

- Withdrawal of consent: the patient, the patient's authorised representative, independent physician, or designated individual who had provided initial consent to enter the study may withdraw consent at any time throughout the duration of the trial, without prejudice to future medical care and treatment.
- Retrospective exclusion: If a patient is deemed to not meet one or more of the inclusion/exclusion criteria in retrospect they will be withdrawn from the study.
- Major protocol deviation from the study design by the participant, observed or suspected by the investigator.
- Administrative: the sponsor or monitoring committees decide to terminate or discontinue the study.

 The participant's health would be jeopardised by continued participation and is withdrawn at the discretion of the investigator.

Data collected up to the point of withdrawal will be retained. To safeguard the participants' rights, the minimum personally-identifiable information possible will be used.

Participants will be asked whether samples already collected can be retained for use in the study. Where a participant consents to storage and use of their samples, they will be asked to sign a consent form reflecting this agreement.

Any samples obtained from withdrawn participants who do not consent to storage or use of their samples will be discarded in accordance with the local NHS Trust standard procedures. Samples sent to the central laboratory at Queen Mary University London will also be discarded.

All participants withdrawn from the study will be managed in accordance with the hospital's standard procedures.

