7.2. Study participants

Only patients who have received prehospital care from the London Air Ambulance and are to be conveyed to a study site *or* patients who arrive at a study site by other means e.g. land ambulance or self-presentation *and* require a trauma team activation will be considered for enrolment into the study. Only those patients undergoing surgical intervention will be considered for the collection of muscle tissue.

As the study is investigating the immediate post-injury phase, patients will be recruited into the study before their full list of injuries is known (before they have X-rays, CT scans, angiograms, operations etc). From our trauma database at the Royal Hospital and existing ACIT study cohort we know that using all major trauma activations, with the exclusion criteria listed below, will provide us with a study population with an injury severity distribution of approximately 35% severe injuries, 55% moderate injuries and 7% minor injuries.

The study will, of necessity, include trauma patients who are unable to give consent for themselves and by definition are in an emergency clinical situation. Patients will be assessed for eligibility to enter the trial according to the criteria set out below. If patients are eligible for entry into the study, following initial screening either in prehospital environment or upon arrival in the Emergency Department, they will be enrolled automatically under a waiver of consent. See Ethics (Section 10) for further details.

The study may also include patients whose first language is not English. There is some evidence that patients from different racial groups have altered responses to injury, and excluding them would bias the study in favour of native English-speaking populations.

Patients will be considered eligible for enrolment in this trial if they fulfil all of the inclusion criteria and none of the exclusion criteria detailed below.

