7.4. Exclusion Criteria

Any patient who fulfils any of these criteria will not be considered for inclusion in the study:

- Transfers from other hospitals
- Burns >5% total body surface area
- >120 mins have lapsed since time of injury
- Deemed inappropriate for recruitment by an independent clinician (e.g. mass casualty event or futility)

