11.1 Informed Consent

Our standard operating procedure for obtaining consent is included in Appendix 2. All participants will be enrolled in the study with a waiver of consent due to the emergency nature of the study. Several approaches to obtaining consent will then be used following hospital admission, depending on the mental capacity of the patient and availability of Personal Consultees (relative or friend).

- [1] If a patient is considered to have mental capacity they will be approached directly, and their informed consent requested.
- [2] For patients who lack capacity and where it is not possible to take agreement from a Personal Consultee we will use approaches consistent with the Mental Capacity (England) Act (2005), as below:
- [a] If the patient has capacity, they will be approached.
- [b] If the patient lacks capacity and a personal consultee not available (which is anticipated to be the case in the majority of instances) an independent clinician acting as a professional consultee will be approached within 24hrs of study enrolment to provide consent for the patient to continue in the study. This will usually be a substantive consultant in emergency medicine acting as trauma team leader. The clinician must not be a named local PI or local individual directly involved in the research project and must be of consultant or senior emergency medicine registrar status. In all cases they must have received prior information about the research to enable them to provide advice regarding inclusion in the emergency situation and be included on a log of professional consultees. It is anticipated that this individual will be best placed to advise as they will be aware of the patient's condition and will be the clinician in charge of the immediate clinical care of the patient. Where the trauma team leader is connected with the research project, or unavailable e.g. due to other clinical demands, it is acceptable to ask the opinion of another emergency or trauma physician who is not connected with the research.

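### Section 9.7 lets enrolled patients be withdrawn in retrospect on any criterion, including an undefined futility judgement, so removal can depend on prognosis or early course

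*Protocol*

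**What the plan says.** Protocol section 9.7 lists reasons for withdrawal. One of them concerns eligibility that is reassessed after entry, and it reads: "If a patient is deemed to not meet one or more of the inclusion/exclusion criteria in retrospect they will be withdrawn from the study". The same section keeps data gathered before withdrawal. Participants are asked whether samples already taken may be kept, and samples from withdrawn participants who do not agree are discarded.

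Section 7.4 has four exclusion criteria. Three are matters of fact: transfer from another hospital, burns over 5% of body surface, and more than 120 minutes since injury. The fourth is a judgement: "Deemed inappropriate for recruitment by an independent clinician (e.g. mass casualty event or futility". Neither term is defined further.

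On timing, section 7.2 says "Patients will be assessed for eligibility to enter the trial according to the criteria set out below" and that, if eligible after initial screening, "they will be enrolled automatically under a waiver of consent". It also says that "patients will be recruited into the study before their full list of injuries is known". Section 9.1 uses the term independent clinician for the professional consultee. Section 11.1[b] says that, where the patient lacks capacity and no personal consultee is available (expected in most cases), "an independent clinician acting as a professional consultee will be approached within 24hrs of study enrolment to provide consent" to continuing in the study.

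Section 11.1[f] keeps in the study, on consultee advice or consent, patients who die during follow-up. The ACIT SWIFT appendix repeats the exclusion criteria and the retrospective-exclusion rule, but there the samples of withdrawn participants are discarded without the option to keep them.

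**The concern.** Retrospective exclusion does little harm when it rests on a fact that was fixed at enrolment and only came to light later. A transfer or a wrongly recorded injury time does not depend on how the patient then fares. Futility is different: it is a statement about prognosis, and prognosis becomes clearer as the patient deteriorates. Applying a without-limit retrospective rule to that criterion opens a route by which leaving the cohort can depend on the early clinical course.

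The patients most exposed are those with the deepest shock and coagulopathy, who carry much of the information for Aims 1 to 3. At stake are the primary outcomes in section 6.2 (24-hour blood products; acute organ injury and MODS), 28-day mortality in section 6.3, and the associations between early biomarkers and these outcomes. Section 11.5 says that deaths from haemorrhage and brain injury occur within the first few days, so a late ruling could fall when the outcome is already known or evident.

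**Working it through.** The protocol gives no expected mortality and no power calculation for the main cohort (section 10), so there is no figure to reproduce. The check is mainly a comparison of the text, followed by an illustration.

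**1. Scope of the rule.** Section 9.7 refers to any inclusion or exclusion criterion, so it reaches the fourth criterion in 7.4. It sets no time limit, does not say who decides, and does not require that the criterion was already met at enrolment.

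**2. When the judgement can be made.** Section 7.2 places eligibility before entry. But entry is automatic and precedes full knowledge of the injuries, and no step obtains or records a futility judgement at screening. The only scheduled contact with an independent clinician is the consultee approach, up to 24 hours after enrolment. Under section 9.4.1, air-ambulance patients have a research sample taken before they reach hospital, where the consultee is usually the trauma team leader. The in-retrospect clause then allows a judgement formed later to take effect.

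**3. What is kept and what is not.** Two hypothetical cases:
- Death at hour 6, ruled ineligible afterwards. The recorded transfusions and the death precede withdrawal and are retained.
- Ruled ineligible at hour 4, death at hour 8. The retained data cover 4 of the first 24 hours. Section 9.7 does not provide for recording the death, organ dysfunction or the other 24 − 4 = 20 hours of the transfusion outcome.

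In both cases the sample rule relies on asking the participant. Section 9.7 does not say what happens when a patient withdrawn for ineligibility has died or lacks capacity.

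**4. Fit with 11.1[f].** That item keeps patients who die, but as a matter of consent. Section 9.7 withdraws on eligibility. Neither says which prevails.

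**5. ACIT SWIFT.** The primary outcome there is measured on the single research sample. Discarding it on withdrawal removes that outcome from a comparison between randomised arms.

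**6. Illustration.** Suppose true mortality is m, a share f of deaths is withdrawn and left out of the analysis, and no survivor is. Observed mortality is m' = m(1 − f)/(1 − mf). For m = 0.15 and f = 0.25: 0.1125/0.9625 = 0.117. Both m and f are assumed.

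| Assumed m | f = 10% | f = 25% | f = 50% |
|---|---|---|---|
| 5% | 4.5% | 3.8% | 2.6% |
| 10% | 9.1% | 7.7% | 5.3% |
| 15% | 13.7% | 11.7% | 8.1% |
| 20% | 18.4% | 15.8% | 11.1% |

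For an association: section 5.1 says coagulopathic patients are three to four times more likely to die. Assume 21% against 6%, a ratio of 3.5. If 5% of deaths are left out in the non-coagulopathic group, its mortality becomes 0.057/0.997 = 0.0572. If 20% of deaths are left out in the coagulopathic group, its mortality becomes 0.168/0.958 = 0.175 and the ratio 3.07. If 30%, it becomes 0.147/0.937 = 0.157 and the ratio 2.74. The fall follows from assuming unequal shares.

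**The case against.** A reader might infer that the protocol has futility judged after enrolment and lets early deaths be deleted once the outcome is known. The documents do not support that.
- Section 7.2 puts eligibility before entry, and 7.4 speaks of recruitment. The natural meaning of the retrospective clause is late discovery that a criterion had already been met. A futility ruling after enrolment is an inference.
- The contact within 24 hours concerns consent to continue. It is not described as an eligibility ruling.
- Section 9.7 retains data up to withdrawal, so a death already recorded stays on the database. Section 11.1[f] shows an intention to keep patients who die.
- Section 11.1 requires independence of the consultee: "The clinician must not be a named local PI or local individual directly involved in the research project".
- Who counts in the analysis could be settled in an analysis plan that is not shown.
- The sizes rest on assumption, and even the direction for 24-hour transfusion is uncertain, because early death cuts transfusion short.

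Most of this stands, and it rules out the stronger reading. It does not close the gap. The intended meaning of the clause is not written into it. Independence limits motive but does not stop the ruling depending on the patient's course, and 9.7 does not say that this clinician makes the retrospective decision. Section 11.1[f] governs consent, not eligibility. An analysis plan can define the analysis set, but it cannot recover follow-up that stopped or samples that were discarded.

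**Conclusion.** The point holds as a defect in the rule, not as evidence of deletion. As written, 9.7 allows, and on its wording requires, withdrawal of a patient later deemed to fail a prognosis-based criterion, with no limit on when that is decided. Later outcomes are not provided for, samples may be lost, and the conflict with 11.1[f] is unresolved.

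This rests on two readings: that the rule covers all four criteria, as its wording says, and that nothing in the protocol confines the futility judgement to screening. The size of any bias cannot be estimated from the protocol; the figures above show only how it would scale under assumed shares. The change is worth making because it is specific and nearly free, and because the loss could not be repaired at analysis.

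**What to change.** In section 9.7:
- Limit retrospective exclusion to the three factual criteria (transfer, burns over 5%, more than 120 minutes since injury), as they stood at enrolment.
- State that a clinician-judgement or futility ruling made after enrolment does not remove a patient from the cohort or from outcome collection, unless consent or consultee agreement is declined.
- Require the time and reason of each such ruling to be logged, and exclusions to be reported by criterion with timing and vital status.
- Align the text with 11.1[f].

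Make the same change in the matching exclusion and withdrawal text of the ACIT SWIFT appendix. The judgement need not be forced to precede the first research sample, which for air-ambulance patients is taken before hospital arrival.

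The cost is a few sentences and minor logging. A few patients with a very poor prognosis stay in the data set.

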9.8. End of Study Definition

Patients are followed up when in hospital daily until day 28, death or discharge (whichever occurs sooner). If patients remain in hospital beyond day 28, their electronic records will be periodically reviewed remotely until discharge to enable collection of any outstanding endpoint data. End of study is at 12 months after completion of EQ5D (adults) or PedsQL (paediatrics) patient questionnaire.

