- [e] If the patient regains capacity but decides they do NOT wish to remain in the trial we will ask the patient to clarify one of the following: [i] they wish to be removed from the trial, decline any further tissue sampling or data collection and wish for all tissue samples already collected to be destroyed in accordance with local hospital policy. A withdrawal form will be completed. [ii] they do not consent to further tissue sampling but consent to the use of tissue samples that have already been collected. Agreement to tissue storage and use for the study will be documented on the consent form. All data collected up to the point of withdrawal will be retained.

- [f] Patients who die during the follow up period or do not regain mental capacity, will be included in the study based on the advice provided by the personal consultee and/or professional consultee. In cases where the subject dies before our attempt to obtain consent from the patient or the personal consultee, the patient will remain in the trial based on the consent obtained by the professional consultee and we will not attempt future telephone contact with relatives/personal consultee in order to minimise stress and anxiety associated with the unexpected and traumatic death of their relative / next of kin.
- [g] In general, the same procedures and principles will apply to the recruitment of paediatric patients with parents or legal guardians providing consent for children aged under 16 years who lack capacity. Paediatric patients who are Gillick competent will give consent for their own involvement. Wherever appropriate children will be involved in the discussion (with parents or legal guardians) regarding consent to use their samples and data. Discretion will be applied by the recruiting member of the research team regarding approaching a parent or legal guardian at all times, particularly during initial screening and recruitment in order to avoid causing undue stress and anxiety. Advice will be taken from the independent clinician in cases of uncertainty. Procedures for paediatric consent are detailed fully in appendix 2.

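### Section 9.7 lets an investigator withdraw a patient from the whole study and does not say that routine outcome data continue to be collected

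*Protocol*

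**What the plan says.** After the participant's own right to withdraw, Protocol section 9.7 adds: "Additionally the PI may withdraw the participant". Two of the listed reasons rest on the investigator's judgement. One is that the participant's "health would be jeopardised by continued participation and is withdrawn at the discretion of the investigator". The other is "Major protocol deviation from the study design by the participant, observed or suspected by the investigator". Both are listed as reasons for withdrawal from the study, not from particular procedures. One sentence on data serves every reason: "Data collected up to the point of withdrawal will be retained". The section also states a general aim: "Every reasonable effort will be made to maintain protocol compliance and to retain patient participation in the study".

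Section 11.1 has the same data rule for people who decline to go on: "All data collected up to the point of withdrawal will be retained".

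On the source of the daily follow-up data, section 9.4.4 says: "All of this data (aside from organ dysfunction scores outside of the critical care unit) is routinely collected". It adds that no extra monitoring is needed. Section 9.8 provides that, for patients still in hospital after day 28, "their electronic records will be periodically reviewed remotely until discharge".

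The ACIT SWIFT sub-study protocol in Appendix 4 repeats both investigator-led reasons and the data sentence under its own patient withdrawal heading.

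**The concern.** In this cohort the physical research procedures are blood draws and, in some adults, muscle biopsies. If taking part might harm a patient, that is a reason to stop those procedures. It is not a reason to stop reading the hospital record. Section 9.7 has only one kind of exit, from everything, so a site following it would stop both.

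At stake are one of the two primary outcomes in section 6.2 (acute organ injury and MODS) and, from section 6.3, 28-day mortality and need for organ support. A decision to withdraw on health grounds could plausibly be related to these outcomes, so the missing values may not be a random subset. No analysis plan can recover outcomes that were never collected, so the rule belongs in the protocol.

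**Working it through.** **Step 1. Does outcome collection stop?** The Protocol never says so in terms, but three places point that way.
- Section 9.7 speaks of withdrawal from the study and keeps data only up to that point.
- Section 11.1, item [c], describes staying in the trial as blood tests and data collection to day 28 together.
- Section 11.1, item [e], gives a patient who declines only further tissue sampling the same cap on data. Even there, no option stops samples while outcomes continue.

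The natural reading is that collection ends.

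**Step 2. What could still be collected without touching the patient?**

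| Outcome | Available from routine records? |
|---|---|
| Blood products in 24 hours | Yes; largely complete before most withdrawals could occur |
| Organ scores in critical care | Yes (9.4.4) |
| Organ scores on the ward | No (stated exception in 9.4.4) |
| Infection, thrombotic events | Yes (9.4.4) |
| Deaths during the in-hospital follow-up | Yes (9.4.4 follows patients to day 28, discharge or death) |
| EQ-5D, GOS-E, PedsQL | No (questionnaires, 9.4.5 and 9.6) |

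Most, but not all, of the day-28 outcome data could continue.

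**Step 3. How large could the loss be?** There is no figure in the plan to reproduce: section 10 says a power calculation does not apply, and neither a withdrawal rate nor a MODS risk is given. The following is for scale only.

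Inputs: N = 5,000 (section 7). Assumed: true risk p of 10%, 20% or 30%; share w withdrawn by the investigator before the event is recorded, 1%, 3% or 5%; risk r among those withdrawn, two or three times p.

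- Observed risk = (p − w·r)/(1 − w)
- Bias = w·(p − r)/(1 − w)
- SE = √(p(1 − p)/5,000)

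Example: p = 0.20, w = 0.03, r = 0.60 gives (0.20 − 0.018)/0.97 = 0.1876. The bias is −1.24 percentage points against an SE of 0.57.

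| p | w | Bias, r = 2p (points) | Bias, r = 3p (points) | SE (points) |
|---|---|---|---|---|
| 10% | 1% | −0.10 | −0.20 | 0.42 |
| 10% | 3% | −0.31 | −0.62 | 0.42 |
| 10% | 5% | −0.53 | −1.05 | 0.42 |
| 20% | 1% | −0.20 | −0.40 | 0.57 |
| 20% | 3% | −0.62 | −1.24 | 0.57 |
| 20% | 5% | −1.05 | −2.11 | 0.57 |
| 30% | 1% | −0.30 | −0.61 | 0.65 |
| 30% | 3% | −0.93 | −1.86 | 0.65 |
| 30% | 5% | −1.58 | −3.16 | 0.65 |

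At 1% withdrawn, every bias is below one SE. At 5%, every bias exceeds one SE.

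**Step 4. Is the direction fixed?** No. The bias is negative only if r > p. With p = 0.20, w = 0.03 and r = 0.10 it is 0.03 × 0.10/0.97 = +0.31 points.

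**The case against.** The strongest reply is that the health clause is narrow. It concerns harm from taking part, not a patient getting sicker. Sections 11.3.1, 11.3.2 and 11.6 describe that harm as bruising, needle puncture and minimal biopsy risk, so the clause should rarely be used. Section 11.1, item [f], keeps patients who die or never regain capacity. The deviation clause covers only major deviations by the participant, which a ventilated patient can hardly commit. This stands, and it limits the size of the problem. It does not remove the problem, because item [f] deals with consent and does not govern a withdrawal made by the investigator.

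A reader might infer more than the documents support:
- **That the sickest patients drop out.** Neither clause is triggered by severity, and nothing ties the deviation reason to severity at all.
- **That MODS incidence must be understated.** That holds only if withdrawn patients carry above-average risk (step 4).
- **That biomarker associations shrink towards the null.** If withdrawal depended on outcome alone, the odds ratio would be unchanged. If it depended on outcome and biomarker together, the bias could go either way.
- **That missing-at-random methods must fail.** Injury severity, admission physiology and earlier organ scores are recorded and might explain part of the loss.
- **That the study needs only routine records.** Ward organ scores and questionnaires are exceptions, and the remote review in section 9.8 is written only for patients in hospital beyond day 28.

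**Conclusion.** The point holds as a gap in the withdrawal rule. On its natural reading, section 9.7 ends outcome collection for two investigator-led reasons when only research procedures need to end, and no refusal by the patient or consultee is required. The same wording recurs in the ACIT SWIFT sub-study protocol.

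The loss may be related to outcome, but its size and direction cannot be stated from the Protocol. Under the assumed values above it ranges from 0.1 to 3.2 points of MODS incidence. The lower end is the more plausible, given how small the Protocol says the risks of participation are. The case for change rests on the loss being avoidable at almost no cost, not on evidence of a large bias. Label: cheap improvement.

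**What to change.** Amend section 9.7 so that, for the health and deviation reasons:
1. the investigator's decision ends research procedures (blood and muscle sampling) only;
2. outcome data available from routine records continue to be collected to day 28, on the existing follow-up schedule, unless the patient or consultee refuses;
3. the date and reason are recorded, and the numbers are reported by reason.

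Leave unchanged the investigator's discretion to stop sampling, the retrospective exclusion of ineligible patients, and termination by the sponsor or monitoring committees.

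Make the matching change in the patient withdrawal text of the ACIT SWIFT protocol. Clinical outcomes there come from the SWiFT trial, so the sentence should say that linked SWiFT data continue to be used on the same condition.

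The cost is a few sentences, a field on the withdrawal form, and a little record review for a few patients. No visits, samples or patient contacts are added.
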